10.3 Subject Information and Informed Consent

The Investigator will obtain freely given written consent from each subject after an appropriate explanation of the aims, methods, anticipated benefits, potential hazards, and any other aspect of the study which is relevant to the subject's decision to participate. The informed consent form must be signed, with name and date and time noted by the subject, before the subject is exposed to any study-related procedure, including Screening tests for eligibility.

For subjects not capable of giving legal consent, written consent must be obtained from the LAR.

The Investigator will explain that the subjects are completely free to refuse to enter the study or to withdraw from it at any time, without any consequences for their further care and without the need to justify. The Investigator will complete the informed consent section of the CRF for each subject enrolled.

Each subject will be informed that his/her medical (source) records may be reviewed by the study monitor, a quality assurance auditor, or a health authority inspector, in accordance with applicable regulations, and that these persons are bound by confidentiality obligations.

10.4 Protocol Amendments

Any prospective change to the protocol will be agreed upon between the Investigator (Coordinating Investigator in multi-center studies) and the Sponsor prior to its implementation. Any such amendments will be submitted to the competent IEC/IRB and/or competent authority responsible as required by applicable regulations.

IEC/IRB approval will, at a minimum, be requested for any change to this protocol which could affect the safety of the subjects, the objective/design of the study, any increase in dosage or duration of exposure to the IMP, an increase in the number of subjects treated, the addition of a new test or procedure, or the dropping of a test intended to monitor safety.

10.5 Confidentiality of Subject Data

The Investigator will ensure that the subject's confidentiality is preserved. On CRFs submitted to the Sponsor, the subjects will not be identified by their names, but by a unique subject identifier.

Transmission of any confidential subject documents from the investigative site to the Sponsor's 3rd party designee (eg, consent forms, source records, etc.) will occur via a secure cloud-based portal with advanced security features such as audit trails and two-factor authentication upon each log-in. This usage is compliant with the FDA Guidance on Conducting Clinical Trials during the COVID-19 Public Health Emergency (dated 03Jun2020). Subjects have consented to the recording and inspection of their personal data via the informed consent form, by the Sponsor or designee, in addition to ethics committees, national and international competent authorities and the FDA.

11 QUALITY CONTROL AND QUALITY ASSURANCE

11.1 Periodic Monitoring

Due to the current COVID-19 pandemic travel and hospital visitation restrictions, most hospitals do not permit monitors to visit the sites or pharmacies to conduct in-person study monitoring and data review. In order for the Sponsor to maintain oversight of the study data investigators must make study source records available for remote review by the study monitor in compliance with local and federal guidelines. Data monitoring will be conducted on an ongoing basis.

If in-person monitoring visits become possible, the monitor will review all study-related source data/records, verify the adherence to the protocol and the completeness, correctness, and accuracy of all CRF entries compared to source data. The Investigator will cooperate with the monitor to ensure that any discrepancies identified are resolved.

The monitor must be given direct access to source documents (original documents, data, and records). Direct access includes permission to examine, analyze, verify, and reproduce any records and reports that are important to the evaluation of the clinical study. Source data will be available for all data in the CRFs, including all laboratory results.

The Clinical Monitoring Plan will describe the requirements for remote and in-person monitoring procedures.

11.2 Audit and Inspection

The Investigator will make all study-related source data and records available to a qualified quality assurance auditor mandated by the Sponsor, or to IEC/IRB/regulatory inspectors, after reasonable notice. The main purposes of an audit or inspection are to confirm that the rights and welfare of the subjects have been adequately protected, and that all data relevant for the assessment of safety and efficacy of the IMP have been reported to the Sponsor.

12 REPORTING AND PUBLICATION

12.1 Clinical Study Report

A clinical study report (in accordance with relevant guidelines and the Sponsor's SOPs) will be prepared by the Sponsor after completion of the study. The Coordinating Investigator will approve the final study report after review.

12.2 Publication Policy

The results of this study may be published or presented at scientific meetings.

If this is envisaged by an Investigator, the Investigator agrees to inform the Sponsor and to submit all manuscripts or abstracts to the Sponsor prior to submission to an editorial board or scientific review committee. This will allow the Sponsor to protect proprietary information and to provide comments based on information that may not yet be available to the Investigator.

In accordance with standard editorial and ethical practice, the Sponsor will support publication of multi-center studies only in their entirety and not as individual center data. Authorship will be determined by mutual agreement.

Property of Octapharma. Do not copy or distribute without written permission.

13 LIABILITIES AND INSURANCE

In order to cover any potential damage or injury occurring to a subject in association with the IMP or participation in the study, the Sponsor will contract insurance in accordance with local regulations.

The Investigator is responsible for dispensing the IMP according to this protocol and for its secure storage and safe handling throughout the study.

Property of Octapharma. Do not copy or distribute without written permission.

## LIST OF ABBREVIATIONS

Abbreviation	Description
AE	Adverse Event
CBC	Complete Blood Count
CMP	Comprehensive Metabolic Panel
CoV	Coronaviruses
COVID-19	Coronavirus disease-2019
CRO	Contract Research Organisation
CRP	C-reactive protein
CT	Computerized Tomography
ECMO	Extracorporeal Membrane Oxygenation
eCRF	Electronic Case Report Form
EDC	Electronic Data Capture
FAS	Full Analysis Set
FDA	Food and Drug Administration
FiO2	Fractional Inspired Oxygen
GCP	Good Clinical Practice
HFNC	High-Flow Nasal Cannula
HIT	Heparin Induced Thrombocytopenia
HIV	Human Immunodeficiency Virus
hsCRP	high-sensitivity C-reactive protein
IB	Investigators' Brochure
ICH	International Council for Harmonisation
ICU	Intensive Care Unit
IDMC	Independent Data Monitoring Committee
IEC	Independent Ethics Committee
Ig	Immunoglobulin
IL	Interleukin
IMP	Investigational Medicinal Product
IMV	Invasive Mechanical Ventilation
IND	Investigational New Drug

INR	International Normalized Ratio
ITT	Intent-To-Treat
IV	Intravenous
IVIG	Intravenous Immunoglobulin
LDH	Lactic acid dehydrogenase
LOCF	Last Observation Carried Forward
MedDRA	Medical Dictionary for Regulatory Activities
MQoL-SIS	McGill Quality of Life Single-Item Scale
NCI-CTCAE	National Cancer Institute-Common Terminology Criteria for Adverse Events
NIV	Non-Invasive Mechanical Ventilation
PaO2	Arterial Oxygen Partial Pressure
PP	Per Protocol
PT	Prothrombin Time
PTT	Partial Thromboplastin Time
RNA	Ribonucleic acid
RT-PCR	Reverse Transcription Polymerase Chain Reaction
QoL	Quality of Life
SAE	Serious Adverse Event
SAF	Safety Analysis Set
SAP	Statistical Analysis Plan
SARS	Severe Acute Respiratory Syndrome
SDV	Source Data Verification
SmPC	Summary of Product Characteristics
SOC	Standard of Care
SOP	Standard Operating Procedure

## 1. Introduction

This statistical analysis plan (SAP) expands the analysis plan in *Section 9 Statistical Methods and Sample Size* of the study protocol “Efficacy and Safety of Octagam 10% Therapy in COVID-19 Patients with Severe Disease Progression” authored by the sponsor (Octapharma Inc) dated January 27, 2021.

Changes to the previously approved SAP are the following:

- The interim analysis has been removed, due to an unexpected acceleration in enrollment. DMC meeting schedules have been described as per actual conduct.
- Secondary endpoints have been updated to reflect the latest protocol version.
- Missing data imputation rules have been revised to allow for the incorporation of additional subject information with respect to establishing the clinical status of a subject at each visit

The scope of analysis provided in this SAP includes: the three scheduled Independent Data Monitoring Committee (IDMC) data reviews and the final analysis after Day 33 of the last subject’s enrollment.

Note that after completion of the core 33-day trial, all subjects will be followed for a one-year period by means of a registry database; subjects will be contacted every 3 months ( $\pm 14$  days) for their health status and any residual health effects from COVID-19 or the study treatment. Analysis of this one-year follow-up registry data is not within the scope of this SAP but will be submitted as a supplement to the core study data once all subjects have completed the year of follow-up.

## 2. Study Objectives and Endpoints

### 2.1 Primary Objective

The primary objective of this study is to determine if high-dose Octagam 10% therapy will stabilize or improve clinical status in subjects with severe COVID-19 during the first seven days following treatment commencement.

#### 2.1.1 Primary Endpoints

- Proportion of subjects with stabilized or improved clinical status at Day 7 on at least one category on a 6-point clinical status scale.
- Change from Baseline (Day 1) at Day 7 in terms of the 6-point clinical status scale (descriptive analysis).

Clinical status categories will be defined as:

1. Hospital discharge or meet discharge criteria (discharge criteria are defined as clinical recovery, i.e., no fever, respiratory rate, oxygen saturation return to normal, and cough relief).
2. Hospitalization, not requiring supplemental oxygen.
3. Hospitalization, requiring supplemental oxygen (but not non-invasive mechanical ventilation (NIV)/high-flow nasal cannula [HFNC]) as defined by A-a Gradient < 150 mmHg.
4. Intensive Care Unit (ICU)/hospitalization, requiring NIV/HFNC therapy, as defined by A-a Gradient  $\geq$  150 mmHg.
5. ICU, requiring extracorporeal membrane oxygenation (ECMO) and/or IMV.
6. Death.

A subject meets the success criteria of stabilization or improvement if the clinical status category on Day 7 is not worse than the clinical status category at Baseline (Day 1 prior to IMP infusion).

## 2.2 Secondary Objectives

### Key Secondary Efficacy Objectives

- To compare the length of hospital stay in subjects treated with *Octagam 10%* compared to those that received placebo through Day 33.
- To determine if high-dose *Octagam 10%* therapy will stabilize or improve clinical status in subjects with severe COVID-19 during the 14 days following treatment commencement.
- To compare the cumulative duration of IMV in subjects treated with *Octagam 10%* compared to those that received placebo through Day 33.
- To compare the cumulative incidence of severe progression in subjects treated with *Octagam 10%* compared to those that received placebo at Day 33.
- To compare cumulative duration of time in ICU in subjects treated with *Octagam 10%* compared to those that received placebo at Day 33.
- To compare cumulative mortality in subjects treated with *Octagam 10%* compared to those that received placebo at Day 33.

### Other Secondary Efficacy Objectives

- To determine if high-dose *Octagam 10%* affects severe acute respiratory syndrome from Coronavirus 2 (SARS-CoV-2) infection status at Day 7.

- To determine if high-dose *Octagam 10%* therapy will improve clinical status in subjects with severe COVID-19 during the 14 days following treatment commencement.
- To compare the cumulative incidence of IMV in subjects treated with *Octagam 10%* compared to those that received placebo through Day 33.
- To compare the time to recovery in subjects treated with *Octagam 10%* compared to those that received placebo through Day 33.
- To compare the time to first improvement in clinical status in subjects treated with *Octagam 10%* compared to those that received placebo through Day 33.

### **Safety Objectives**

- To describe the safety of Octagam 10% compared to placebo when administered to subjects with severe COVID-19.

#### **2.2.1 Secondary Endpoints**

### **Key Secondary Efficacy Endpoints**

- Length of hospital stay (time to discharge) through Day 33
- Proportion of subjects with maintenance or improvement by at least one category on the 6-point clinical status scale on Day 14.
- Cumulative duration of IMV through Day 33
- Proportion of subjects with severe progression defined as requiring ECMO, IMV and/or have died through Day 33
- Length of time in ICU from randomization through Day 33
- Mortality rate through Day 33.

### **Other Secondary Efficacy Endpoints**

- Results of reverse transcription polymerase chain reaction (RT-PCR) for SARS-CoV-2 from nares/throat swab and/or sputum and/or lower respiratory tract sample on Day 7.
- Proportion of subjects admitted to ICU from randomization through Day 33
- Proportion of subjects with improvement on Days 7, 14, 21, 33
- Proportion of subjects requiring IMV by Day 33.
- Time to recovery through Day 33 where recovery is defined as a clinical status of 1 or 2

- Time to first improvement in clinical status through Day 33

### **Safety Endpoints**

- Incidence of all adverse events (AEs)
- Incidence of AEs considered related to the Investigational Medicinal Product (IMP)
- Incidence of serious adverse events (SAEs)
- Clinical laboratory parameters
- Vital sign parameters
- Radiological findings (chest computerized tomography [CT]/chest X-ray)

### **2.3 Exploratory Objectives**

- To compare changes in SpO2 on room air from Baseline (Day 1) to all available on-study time points up to Day 33 in subjects treated with Octagam 10% compared to those that received placebo.
- To compare changes in the Modified Borg Dyspnea Scale from Baseline (Day 1) to Days 7, 14, 21, and 33 in subjects treated with Octagam 10% compared to those that received placebo.
- To compare changes in Quality of Life (McGill Quality of Life Single-Item Scale, MQoL-SIS) score from Baseline (Day 1) to Days 7, 14, 21 and 33 in subjects treated with Octagam 10% compared to those that received placebo.

#### **2.3.1 Exploratory Endpoints**

- Improvement of SpO2 on room air from Baseline (Day 1) to Day 33 using trend from all available observed data.
- Modified Borg Dyspnea Scale score at Baseline (Day 1) and on Days 7, 14, 21, and 33.
- MQoL-SIS score at Baseline (Day 1) and on Days 7, 14, 21, and 33.

## **3. Study Design, Procedures, and Analysis Timing**

This is a randomized, double-blind, placebo-controlled, multicenter, Phase 3 study in the US, Russia and Ukraine to evaluate whether high-dose Octagam 10% therapy can stabilize or improve clinical status in subjects with severe COVID-19 disease.

Following screening procedures, eligible subjects will be randomized in a 1:1 ratio to receive either Octagam 10% in a dose of 2 g/kg over 4 days (0.5 g/kg/day), or an equivalent volume of saline (placebo).

The infusion will be administered over a period of 2 hours per day over a total of 4 consecutive days. The first dosing will take place within 24 hours of the Screening Visit.

Approximately 208 male or female adult subjects will be recruited so that approximately 104 subjects in each treatment arm will complete the study. Each subject's participation will last a total of approximately 33 days, including 29 days for safety follow-up, followed by a one-year registry follow-up.

The final primary analysis will take place after database lock.

The primary analysis may also be conducted prior to database lock but after the last subject enrolled completes their Day 33 visit (or discontinues). If conducted, this analysis would be distributed to a limited unblinded team to evaluate the need to submit an emergency use application. Full details on this process will be provided in an unblinding plan and the clinical study report.

Upon end of study follow up, an end of study analysis may be conducted.

#### **4. General Analytic Considerations**

Unless otherwise mentioned:

- Number of subjects in the defined population and number of subjects with available data will be provided.
- Continuous variables will be summarized using descriptive statistics such as mean, standard deviation, median, quartiles, minimum, and maximum, and 95% confidence interval.
- Categorical variables (e.g., gender, race, etc.) will be provided using frequency tabulations.
- Individual listings will be provided to support the descriptive analyses.
- Baseline is defined as the last observation prior to randomization for the analysis of efficacy endpoints. Baseline is defined as the last observation prior to first administration of study drug for the analysis of safety endpoints.

##### **4.1 Missing Data**

The latest patient status available prior to Day 7 will be used to determine clinical status in the absence of a clinical status assessment. If a death date is prior to Day 7, clinical status at Day 7 will be identified as a 6. Otherwise, if a subject's last status reflects that they were in the ICU and receiving ECMO and/or IMV, clinical status will be imputed as a 5. Otherwise, if a subject's last status reflects that they were in the ICU and not receiving ECMO and/or IMV, clinical status will be imputed as a 4. If the LOCF clinical status value for a patient is higher than these imputed values or if a subject status cannot be derived based on available information on ECMO, IMV, or ICU status, the last observation carried forward (LOCF)

will be used to impute patient values. Subjects with no post-baseline clinical status assessment, or prohibited medication use, on or prior to Day 7 will be imputed as failure.

An imputation analogous to the primary endpoint will be performed for the secondary endpoint of clinical status at Day 14.

For the secondary endpoint length of hospitalization, Subjects who are still hospitalized as of Day 33, subjects with missing end dates due to withdrawal, subjects with unusable end dates due to prohibited medication use, or those who died on/prior to Day 33 will be censored at Day 33. Discharge occurring on or after the start date of prohibited medication use will not be considered an event.

Cumulative duration in ICU will be imputed similarly, unless a patient has a useable discharge date (e.g. not occurring prior to prohibited medication use); in this case, the ICU discharge date will be set to the hospital discharge date. If a subject's last assessment identifies that IMV was used (and has no usable end date), the date on which it is no longer used will be assumed Day 33 unless the subject is discharged from the hospital prior to Day 33. If this occurs, the hospital discharge date will be used. IMV end dates will be imputed similarly, assuming that IMV ceases at the time of ICU discharge. Hospitalization, ICU, and IMV end dates for subjects who died prior to Day 33 during these events (e.g. after ICU admission or IMV initiation) will result in assumed end dates of Day 33 for endpoint analyses, so long as prohibited medication was not administered. Any dates on or after the start date of prohibited medication use will be considered unusable for imputation purposes; ongoing hospitalization, ICU, or IMV at the time of medication use will default to extrapolation to Day 33.

For the key secondary endpoint involving severe progression (ECMO, IMV, and death), subjects who withdrew early from study prior to Day 33 without evidence of events will be treated as not having the event. Sensitivity analyses will be conducted (1) treating them as failures (having the event at their last study visit) and (2) excluding them from the analyses. An additional analysis of these endpoints will be provided, treating prohibited medication use prior to Day 33 as an event, as well as allowing for status (event or success) without regard to prohibited medication use.

The outcomes for safety assessment and for additional efficacy analysis as well as exploratory endpoints will not be imputed if data is missing.

Please also refer to the more detailed descriptions in sections 12 to 18 of this SAP for additional details on the handling of missing data for particular endpoints and analyses.

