9.2.5 Handling of Missing Data

In support of the primary and key secondary endpoints of stabilization or improvement in clinical status the following imputation methods will be used. For subjects with clinical status assessment at Baseline (Day 1) and at least one non-missing post-baseline clinical status assessment, last observation carried forward (LOCF) will be used to

impute the missing data at Day 7. However, if there is available data that otherwise indicates events such as death, ECMO or IMV, ICU admittance, occurred after the last non-missing clinical status assessment but on or prior to Day 7, the clinical status will be imputed according to the worst-case of either the LOCF or the clinical information available. Subjects with missing data at Baseline (Day 1) will be imputed as failure. Subjects with no post-baseline clinical status assessment on or prior to Day 7 will be imputed as failure.

Sensitivity analyses will be implemented by assuming all failure (worst case scenario) if subject has missing data at Baseline (Day 1) or Day 7, and where subjects with missing data are excluded.

Missing data for the outcome of clinical status at Day 14 will be imputed in the same fashion as in primary endpoint.

For the key secondary endpoint involving severe progression (ECMO, IMV, death, ICU admittance), subjects who withdrew early from study prior to Day 33 without evidence of events will be treated as not having the event. Sensitivity analyses will be conducted (1) treating them as failures (having the event at their last study visit) and (2) excluding them from the analyses. An additional analysis of these endpoints will be provided, treating prohibited medication use prior to Day 33 as an event, as well as allowing for status (event or success) without regard to prohibited medication use.

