Cumulative duration on IMV through Day 33 and is defined as (IMV end date – IMV start date + 1). Subjects who do not require IMV will have a duration set to 0. Subjects who die on or prior to Day 33 or are still on IMV at Day 33, will have a duration set to their actual/projected Day 33 date for the IMV end date, so long as prohibited medication was not administered. If IMV end date is missing but subject is discharged from ICU or hospital, then IMV end date will be set to the earlier of the ICU or hospital discharge date. Otherwise, subjects without usable IMV end date information due to withdrawal or prohibited medication use will use a projected Day 33 date for the IMV end date. Comparisons between

treatment arms will be performed using a stratified Wilcoxon-Mann-Whitney (van Elteren) test with age category as a stratification factor.

Proportion of subjects with severe progression will be defined as the proportion that require ECMO, IMV or died prior to Day 33. For this analysis, subjects who use prohibited medication prior to the earliest of progression or Day 33 will not be included in analyses. Hypothesis testing for this endpoint will be conducted as described for the primary endpoint.

Length of time in ICU from randomization through Day 33 includes number of days spent in the ICU from randomization through Day 33 and is defined as [ICU discharge date – (later of ICU admittance date, randomization date) + 1]. Subjects who are not admitted to the ICU will have a duration set to 0. Subjects who die on or prior to Day 33 or are still in the ICU at Day 33, will have a duration set to their actual/projected Day 33 date for the discharge date, so long as prohibited medication was not administered. If ICU discharge date is missing but subject is discharged from hospital, then ICU discharge date will be set to hospital discharge date. Otherwise, subjects without usable ICU end date information due to withdrawal or prohibited medication use will use a projected Day 33 date for the ICU end date. Comparisons between treatment arms will be performed using a stratified Wilcoxon-Mann-Whitney (van Elteren) test with age category and baseline ICU status (In ICU at baseline versus not in ICU at baseline) as stratification factors.

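### SAP 4.1 and Protocol 9.2.5 can give the same subject opposite primary outcomes when the Day 7 clinical status is missing

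*SAP*

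**What the plan says.** SAP 4.1 fills a missing Day 7 status in order. Death gives 6. Category 5 comes next, where the "last status reflects that they were in the ICU and receiving ECMO and/or IMV, clinical status will be imputed as a 5". Failing that, if the "last status reflects that they were in the ICU and not receiving ECMO and/or IMV, clinical status will be imputed as a 4". LOCF is used in two situations only. One is that it is worse than the value assigned in this way. The other applies "if a subject status cannot be derived based on available information on ECMO, IMV, or ICU status". Day 14 is handled by analogy. Under SAP 4.6, an assessment made outside the window (24 hours for Day 7, 48 hours for Day 14) also counts as missing.

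Protocol 9.2.5 starts from LOCF and replaces it with a worse value when other data show "events such as death, ECMO or IMV, ICU admittance, occurred after the last non-missing clinical status assessment" and no later than Day 7. Two features differ from the SAP: the event must be new since the last score, and ECMO or IMV counts without reference to the ICU.

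The scale (SAP 2.1.1, Protocol 3.1.1) describes category 3 as "Hospitalization, requiring supplemental oxygen (but not non-invasive mechanical ventilation (NIV)/high-flow nasal cannula [HFNC"), with an A-a gradient below 150 mmHg. Category 4 is NIV or HFNC with a gradient of 150 mmHg or more, either in an ICU or elsewhere in hospital. Category 5 is ECMO or IMV and its label names the ICU. Success means a Day 7 category no worse than baseline.

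SAP 20 states that no change from the protocol applies. The SAP's introduction ties it to the protocol dated January 27, 2021, which is the version under review.

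**The concern.** Being in an ICU does not separate category 3 from category 4, because category 4 covers both locations and the dividing line is type of support and A-a gradient. SAP 4.1 nevertheless uses ICU location alone to assign a 4. It also has no timing condition, so an ICU stay that was already part of the subject's picture when last scored as 3 is treated like a deterioration. In the other direction, NIV is not among the data the rule uses, and a 5 needs ICU and ECMO or IMV together.

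SAP 13 makes Section 4.1 the imputation method for the primary analysis, and Day 14 stabilization or improvement is second in the key secondary hierarchy. The two governing documents therefore prescribe different primary outcomes for some subjects, and the SAP does not say so.

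**Working it through.** **Rules compared.** Expected baseline categories are 3 and 4: inclusion criterion 5 requires supplemental oxygen and exclusion criterion 7 bars IMV. All rows below have Day 7 missing and at least one post-baseline score. The support column takes conventional oxygen = 3, NIV/HFNC = 4, ECMO/IMV = 5 and sets the A-a gradient aside.

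| Baseline | Last score | Other information | SAP 4.1 | Protocol 9.2.5 | By support |
|---|---|---|---|---|---|
| 3 | 3 | Already in ICU when last scored, conventional oxygen, no escalation | 4, failure | 3, success | 3, success |
| 3 | 3 | NIV started on a ward after last score | 3, success | NIV not named in an open-ended list | 4, failure |
| 3 or 4 | same as baseline | IMV recorded outside an ICU after last score | LOCF, success (literal reading) | event counted, failure | 5, failure |
| 4 | 4 | In ICU, no ECMO or IMV | 4, success | 4, success | success |

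Row 1 is a direct conflict between the documents. It also arises if the last score was 2, that is, after a recorded improvement. Row 4 shows that the ICU branch creates false failures only at baseline 3. Row 2 is a gap in the SAP rule that the protocol's list does not clearly close. Row 3 is a second conflict, in a rarer situation.

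Subjects in the ICU at baseline are foreseen: SAP 14 stratifies the ICU-time analysis by "baseline ICU status (In ICU at baseline versus not in ICU at baseline"). The documents do not say how many of them are in category 3.

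**Size per subject.** With 104 per arm, one changed outcome moves that arm's rate by 1/104 = 0.96 percentage points.

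**Planning figures (Protocol 9.1).** 176/(1 − 0.15) = 207.1, rounded up to 208, as stated. With rates 0.60 and 0.80 and two-sided alpha 0.05, power = Φ{[d − 1.96·√(2p̄(1−p̄)/n)] / √[(p₁(1−p₁)+p₂(1−p₂))/n]}. At n = 88 per arm: (0.20 − 0.1354)/0.0674 = 0.958, power 0.831, which meets the stated minimum of 80%. At n = 104: (0.20 − 0.1246)/0.0620 = 1.217, power 0.888.

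**Illustration of power loss (assumed inputs).** Take m = 0.15 missing at Day 7, borrowing the planning drop-out rate, and let a share f be misclassified equally in both arms. The documents give no value for f; the range 10% to 50% is an assumption.

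- True successes turned into failures, p′ = p(1 − mf). At f = 0.10 the rates are 0.591 and 0.788, difference 0.197, power 0.872. At f = 0.50 they are 0.555 and 0.740, difference 0.185, power 0.802. The number affected is 208 × 0.15 × 0.70 × f, about 2 to 11 subjects.
- True failures turned into successes, p′ = p + (1 − p)mf. At f = 0.10 the rates are 0.606 and 0.803, difference 0.197, power 0.881. At f = 0.50 they are 0.630 and 0.815, difference 0.185, power 0.851. The number affected is 208 × 0.15 × 0.30 × f, about 1 to 5 subjects.

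The upper end is an outer bound. A false failure needs baseline 3, an ICU bed, no escalation and a missing Day 7 all together.

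**The case against.** Several counter-arguments have force.

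- The scale is not purely one of respiratory support. Categories 3 and 4 carry an A-a gradient cut, and the labels of 4 and 5 name the ICU. An ICU subject on a mask may have a gradient of 150 mmHg or more. The gradient is measured only at baseline and Day 7 (Protocol 7.2.4), so any rule for a missing Day 7 is a proxy, and the protocol uses ICU admission as one too. This stands. A reader might infer that every ICU subject imputed as 4 is misclassified; the documents do not support that. What remains is the subject whose every recorded score is 3 and who has no new event.
- IMV outside an ICU is an edge case. Category 5 is labelled as ICU care, SAP 4.1 assumes that IMV stops at ICU discharge, and with IMV on record one could argue that the status is derivable and LOCF is not triggered. This also stands, so the row 3 case rests on a literal reading. NIV on a ward does not share the weakness, because category 4 explicitly allows it.
- A reader might infer that success would track bed allocation that varies between the US, Russia and Ukraine and so bias the comparison. The documents say nothing about such differences. Randomization is in permuted blocks within site (Protocol 9.3) and the study is blinded, so ICU practice should be balanced between arms.
- Safeguards exist: complete-case and worst-case analyses (SAP 13) and settlement of final imputation at blinded review (SAP 7). They limit the damage. However, the first drops the imputed subjects, the second fails them all, and the review sets no rule; none applies the protocol's method to the primary result.
- The SAP's introduction says that imputation rules were revised to use more subject information, so a change was deliberate. But that describes a change from the previous SAP, not a declared departure from the protocol.

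**Conclusion.** The point holds as a conflict between the two documents in the primary endpoint and, by analogy, at Day 14. For a baseline category 3 subject already in the ICU when last scored 3 and with no later escalation, SAP 4.1 gives failure and Protocol 9.2.5 gives success. The SAP rule can also err the other way, by leaving a baseline 3 subject with later ward NIV as a success and, more rarely, a subject with IMV recorded outside an ICU.

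The size is 0.96 percentage points of one arm's rate per affected subject. The number affected is unknown. It is confined to missing or out-of-window assessments with at least one post-baseline score, because subjects without one are failures under both documents. The expected consequence is misclassification and some loss of power. A systematic shift between arms, or a shift of several percentage points in the treatment difference, would need facts that the documents do not contain. The correction should be made before unblinding because the rule defines the primary outcome and the mismatch is undeclared.

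**What to change.** Rewrite SAP 4.1 to follow Protocol 9.2.5: impute the worse of LOCF and any event recorded after the last non-missing assessment and on or before Day 7.

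- Death: 6.
- ECMO or IMV, with no ICU condition: 5.
- New ICU admission, or newly recorded NIV: at least 4. Naming NIV makes explicit what the protocol's open list leaves unsaid.
- Already in the ICU when last scored, with no later escalation: keep LOCF.

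Use HFNC only if the eCRF can identify it, because the support list in Protocol 7.2.2 does not name it. Apply the same rule at Day 14. List in SAP 20 any difference from the protocol that is kept on purpose.

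The cost is a paragraph of SAP text and a small change to the derivation. No new data are needed for the NIV and IMV parts: Protocol 7.2.2 has support recorded at each visit and in between when it changes. ICU dates are already required for the ICU-time endpoint.
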